2.1 Study rationale and purpose

The FGFR signaling pathway has critical roles in development, cell proliferation, metabolism and survival (Turner and Grose 2010). Deregulation of FGFR signaling has been implicated in the development of many types of human cancers by resulting in cellular programs that promote tumor progression or resistance to anti-cancer therapies. Furthermore, molecular studies have shown that FGFR signaling exhibits cross-talk with the RAS-MAPK-ERK and PI3K-AKT pathways (Babina and Turner 2017).

The results from two recent clinical studies provide additional support for using Infigratinib in treating patients with solid tumors harboring *FGFR* genetic alterations. In a phase 1 expansion cohort of 67 patients with previously treated metastatic urothelial carcinoma harboring *FGFR3* genetic alterations (fusions and mutations), an overall response rate of 25.4% was observed in patients treated with Infigratinib. An additional 38.8% of patients had stable disease, leading to a disease control rate of 64.2% (Pal et al. 2018). In CInfigratinibX2204 a single-arm, multi-center phase 2 study of 61 patients with advanced cholangiocarcinoma with *FGFR* genetic alterations (n=48 fusions; n=8 mutations; n=3 amplifications) having progression on first-line gemcitabine-containing chemotherapy, Infigratinib treatment produced an overall response rate of 14.8% and a disease control rate of 75.4% (Javle et al. 2018). Progression free survival (PFS) of patients treated with Infigratinib was 5.8 months, which is on par with first-line chemotherapy. Based on the results in these 61 patients, enrollment has been increased to a total of 120 patients to more precisely define response rate, duration of response and PFS.

In summary, genetic alterations in the FGFR gene family occur frequently in different types of human cancers (**Table 1**). To date, the results of pre-clinical and clinical studies support further evaluation of the efficacy of Infigratinib in treating patients with various cancer types, in addition to cholangiocarcinoma and urothelial carcinoma, driven by oncogenic FGFR signaling that result from structural alterations such as fusions as well as other types of activating mutations.

2.2 Rationale for study design

Based on the existing pre-clinical and clinical data described in Section 2.1, the current tissue-agnostic study is designed to evaluate efficacy of Infigratinib when administered as a single agent to patients with genetically selected advanced or metastatic solid tumors through assessment of the overall response rate. The presence of oncogenic *FGFR* fusions or other *FGFR* genetic alterations in cancers are likely to confer sensitivity to Infigratinib. A single arm study evaluating response to Infigratinib and durability of response is an appropriate design in this cancer type-agnostic patient population, which is defined by the presence of a specific targetable genetic alteration (e.g. *FGFR* fusion or activating mutation) rather than histologic classification of cancer (Simon et al. 2016). One of the aims of this study is to further evaluate the efficacy of Infigratinib in solid tumor patients who have had treatment with an alternate *FGFR* inhibitor. Numerous secondary mutations in *FGFR* after treatment with an *FGFR* inhibitor have been reported that confer resistance to therapy (Katoh 2018). It would be important to determine the efficacy of Infigratinib in patients who may have acquired mutations induced by different *FGFR* inhibitors.

In summary, the current study is designed to evaluate the efficacy of Infigratinib in the following patients:

- Patients with different solid tumor types containing *FGFR* fusions
- Patients with different solid tumor types containing other activating mutations in *FGFR*
- Patients with different solid tumor types having received prior therapy with *FGFR* inhibitors

2.3 Rationale for dose and regimen selection

Patients enrolled in this study will receive 125 mg qd of Infigratinib on a 3 week on (21 day) /1 week off (7 day) schedule in 28-day cycles. This dose level and regimen is based on experiences from the CInfigratinibX2101 trial.

The MTD/RP2D from the CInfigratinibX2101 study was identified as 125 mg administered once daily (qd) in continuous 28-day cycles. While dose levels of 100 mg qd and higher were tolerated by patients, the majority of the patients experienced reversible hyperphosphatemia, which led to study drug interruptions. An evaluation of the drug administration records for patients prior to receiving prophylactic phosphate-lowering therapy, indicated that the median time until first dose interruption was approximately 23 days and the median duration of interruption was 7 days. This observation led to the introduction of an expansion arm in the ongoing CInfigratinibX2101 study to evaluate the administration of 125 mg qd on a 3 week on (21 days) / 1 week off (7 days) schedule in 28-day cycles. To date, the majority of patients enrolled in this arm have completed their first cycle of therapy without hyperphosphatemia induced dose interruptions, while maintaining anti-tumor activity.

3. Objectives and endpoints

3.1 Table 2. Primary objectives and endpoints

Primary objectives	Primary endpoints
1. To evaluate the efficacy of single agent Infigratinib in patients with advanced or metastatic solid tumors of any histologic classification with	Overall response assessed by investigator as per RECIST v1.1

FGFR1-3 gene fusions/translocations or other FGFR genetic alterations (with and without prior therapy with different FGFR inhibitor)	
2. To understand response rate and potential for Infigratinib to benefit patients who have FGFR alterations including point mutations, insertions/deletions and amplifications in different solid tumor types.	Overall response assessed by investigator as per RECIST v1.1

3.2 Table 3. Secondary objectives and endpoints

Secondary objectives	Secondary endpoints
1. To further evaluate the efficacy of single agent Infigratinib	Progression free survival, best overall response, disease control rate, overall survival assessed by investigator as per RECIST v1.1
2. To characterize the safety and tolerability of single agent Infigratinib	Safety: Type, frequency, and severity of AEs and SAEs Tolerability: dose interruptions, reductions and dose intensity
3. To evaluate benefit of Infigratinib in patients who have received one prior FGFR inhibitor	Progression free survival, best overall response, disease control rate, overall survival assessed by investigator as per RECIST v1.1

3.3 Exploratory objectives:

Exploratory objective 1: To detect biomarkers of resistance to Infigratinib treatment through tumor sequencing.

- Method: Archival or newly obtained tumor samples will be collected to explore mechanisms of resistance to Infigratinib treatment through analysis of next generation DNA sequencing data from tumor sample at baseline, on-treatment (after completion of 2 cycles) and after the development of disease progression (whenever available). Detailed protocol for tissue acquisition and sequencing is in Section 7.3.2 “Biomarkers and correlative studies”.

Exploratory objective 2: To develop a circulating tumor DNA (ctDNA) or liquid biopsy assay optimized for monitoring response to Infigratinib and detecting emerging resistance mutations to Infigratinib

- Method: Blood samples will be collected at screening and throughout the study for ctDNA analysis to explore correlation with genetic alterations in tumor tissue at baseline, clinical response and development of resistance. Detailed protocol for the development of *FGFR* liquid biopsy assay in Section 7.3.2 “Biomarkers and correlative studies”.

4. Study design

4.1 Description of study design

This is a multi-center, open label, single arm phase 2 study evaluating Infigratinib anti-tumor activity in advanced or metastatic solid tumor patients with *FGFR* genetic alterations including gene fusions/translocations, point mutations, and insertions/deletions. Oral, monotherapy Infigratinib will be administered once daily for the first 3 weeks (21 days) followed by one week break of each 28-day cycle. Treatment period will begin on Cycle 1 Day 1 and will continue until disease progression, unacceptable toxicity, withdrawal of informed consent, or death. Patients will be evaluated for tumor response radiographically every 8 weeks until disease progression or discontinuation from study using RECIST v1.1.

As depicted in Figure 1, patient accrual for the current study will occur at The Ohio State University and through clinical sites from institutions that are members of the Oncology Research Information Exchange Network (ORIEN, <http://oriencancer.org/>). OSU is a founding member of ORIEN, which includes eighteen large academic hospital systems with patients who have consented to a common study that includes tumor profiling by next generation sequencing (whole exome and RNAseq), collection of clinical data, and re-contact for potential clinical trials offering therapies that match the genetic alterations in their cancers. Thus, ORIEN provides a mechanism for pre-screening to identify candidate patients with *FGFR* genetic alterations and can help accelerate patient accrual to this study.

Clinical subsites to be determined based on populations of *FGFR*+ patients and interest from ORIEN members. Additional non-ORIEN clinical sites may be identified as well. Regardless of prior research screening, all patients must have had CLIA-certified assay with requisite *FGFR* gene alterations. Additional subsites with active molecular testing for *FGFR* may also be recruited as a clinical subsite.

[figure not shown]

Figure 1. Study schema for phase 2 trial evaluating Infigratinib efficacy in patients with advanced *FGFR*-altered solid tumors with and without prior exposure to alternate *FGFR* inhibitor therapy.

Molecular Eligibility

Documented evidence of *FGFR* genetic alterations with a CLIA-certified assay is required in order to begin study related screening procedures. Evidence can be demonstrated by locally available data (local laboratory or institution-designated sequencing facility). If local data or the results of the central analysis meet inclusion criteria, the patient can proceed with the screening procedures.

Screening

Screening assessments must be completed within 21 days prior to the first dose of study treatment except for the radiological tumor assessment which should be performed within 28 days prior to the first dose.

Treatment period

Treatment period will begin on Cycle 1 Day 1 and will continue until disease progression, unacceptable toxicity, withdrawal of informed consent, or death.

End of treatment (EOT)

The EOT visit occurs within 14-28 days after of the decision to discontinue study treatment. All participating patients must complete this visit even if they had to discontinue prematurely.

Follow-up

All patients will be followed up as described in Section 7.1.6.

30-day safety follow-up period

At a minimum, all patients must complete the safety follow-up assessments 30 days after their last dose of Infigratinib.

Disease progression follow-up period

All patients enrolled in the study who discontinue study treatment for any reason other than disease progression will have a tumor assessment every 8 weeks, until disease progression or the initiation of subsequent anticancer therapies, or death, whichever occurs first.

Survival follow-up period

All patients enrolled in the study will be followed for survival every 4 months for one year after discontinuation of treatment.

4.2 Timing of interim analyses and design adaptations

No formal interim analysis is planned for this study. Safety and efficacy data will be continuously monitored by QED Therapeutics in conjunction with the investigators for decision-making purposes. This is a signal finding study and early stopping rules for efficacy will not be applicable. Substantial safety data is already available for existing Infigratinib study, but will be monitored.

4.3 Assessment of potential mechanisms of resistance

Patients will have mandatory tumor tissue and blood samples collected at baseline, on-treatment (after completion of 2 cycles), and at disease progression to study the mechanisms of drug treatment resistance.

4.4 Definition of end of the study

End of study is defined as the time when the last patient completes the survival follow-up as described in Section 7.1.6 or when the last patient on study has expired, been lost to follow-up, or withdraws consent, whichever occurs first or when the study is terminated early.

The analysis of study data will be based on all patients' data up to the time when all patients have completed at least 6 cycles of treatment or discontinued the study. This will be the cutoff point for the primary clinical study report (CSR). The additional data for any patients continuing to receive Infigratinib, or remain in safety or survival follow-up beyond the cut-off point will be summarized in a final CSR that will be prepared once all patients have either discontinued or completed the study i.e. end of survival follow-up period which is defined as the time when all patients have discontinued study and at least 80% of the patients have died, withdrawn consent, or been lost to follow-up.

4.5 Early study termination

The study can be terminated at any time for any reason by the Principal Investigator for reasons related to efficacy or safety. Should this be necessary, the patient should make every effort to complete their final visit. The same assessments should be performed as described in Section 7.1.4 and Section 7.1.5 for a prematurely withdrawn patient. The investigator may be informed of additional procedures to be followed in order to ensure that adequate consideration is given to the protection of the patient's interests. The investigator will be responsible for informing IRBs and/or ECs of the early termination of the trial.

5. Study population

5.1 Patient population

Adult patients with histologically or cytologically confirmed advanced or metastatic solid tumors with *FGFR1-3* gene fusions/translocations or other *FGFR* genetic alterations will be enrolled (**Figure 1**, Section 4.1). Patients must have received at least one prior regimen and therapies available that are known to confer a clinical benefit consisting of standard of care (SOC) therapy for cancer of a given histology classification or have demonstrated intolerance of SOC therapy. Patients should have had evidence of progressive disease following their prior regimen or if prior treatment was discontinued due to toxicity must have continued evidence of measurable or evaluable disease.

This trial plans to enroll a total of fifty patients, divided into the following 3 cohorts:

- Cohort 1: n=30, *FGFR1-3* fusion+ solid tumors, no prior treatment with FGFR inhibitor
- Cohort 2: n=10, *FGFR1-3* fusion+ solid tumors, must have received prior FGFR inhibitor therapy
- Cohort 3: n=10, *FGFR* mutation+ solid tumors, no prior treatment with FGFR inhibitor

Evidence of *FGFR* genetic alterations must be documented (refer to Section 7.1.1 for further details).

Patients enrolled in this study are not permitted to participate in additional parallel investigational drug or device studies. Patients who do not initially meet all of the inclusion or exclusion criteria may be rescreened for consideration in the trial. If a patient is rescreened, the same patient ID number should be used (see Section 7.1.2.2).

Only patients who have documented evidence *FGFR* genetic alterations will be allowed to enter screening. The investigator or designee must ensure that only patients who meet all the following inclusion and none of the exclusion criteria are offered treatment in the study.

5.2 Inclusion criteria

Patients eligible for inclusion in this study have to meet all of the following criteria:

1. Patients with histologically or cytologically confirmed advanced or metastatic solid tumors of any histologic classification at the time of diagnosis.
2. Written documentation of local or central CLIA-certified laboratory determination of *FGFR* gene fusions/translocations or activating mutations.
3. The study is open to solid tumors in the following cohorts:
 - a. Cohort 1: Solid tumor patients with *FGFR1-3* fusion/translocation (**n, up to 30**) who have progressed on or are intolerant to SOC therapies. Prior therapy with a different *FGFR* inhibitor is not permitted. Cholangiocarcinoma patients are excluded from this cohort (there are multiple competing studies and opportunities for patients to get treatment in other trials).
 - b. Cohort 2: Solid tumor patients with *FGFR1-3* fusion/translocation (**n=10**) who have progressed on or are intolerant to SOC therapies and received treatment with a different *FGFR* inhibitor. Cholangiocarcinoma patients are permitted in this cohort.
 - c. Cohort 3: Solid tumor patients with genetic alterations such as point mutations, insertions/deletions, or amplifications in any *FGFR* gene family member (**n=10**). Prior therapy with a different *FGFR* inhibitor is not permitted. Cholangiocarcinoma patients are permitted in this cohort.
4. Evidence of measurable or evaluable disease according to RECIST Version 1.1.
5. Patients must have received at least one prior SOC regimen for advanced/metastatic cancer. Patient should have had evidence of progressive disease following their prior regimen, or if prior treatment was discontinued due to toxicity must have continued evidence of measurable or evaluable disease. Patients who have received prior treatment with an alternate *FGFR* inhibitor are still eligible for the study.
6. Patients with primary CNS cancer or CNS metastases are excluded (because it is unclear how much CNS penetration the drug has). However, asymptomatic patients with history of successfully treated CNS metastases with surgery or radiation and follow up imaging showing stability, can be eligible.
7. Patients ≥ 18 years of age of either gender.
8. ECOG performance status ≤ 1 (Patients with ECOG performance status of 2 may be considered on a case-by-case basis after discussion with QED Therapeutics).
9. Able to read and/or understand the details of the study and provide written evidence of informed

consent as approved by IRB/EC.

10. Recovery from adverse events of previous systemic anti-cancer therapies to baseline or Grade 1, except for:
 - a. Alopecia
 - b. Stable neuropathy of \leq Grade 2 due to prior cancer therapy
11. Able to swallow and retain oral medication.
12. Willing and able to comply with scheduled visits, treatment plan and laboratory tests.

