7.2 Assessment types

7.2.1 Efficacy assessment

Tumor response will be evaluated locally by the investigator according to the guideline (see Appendix 3) based on the Response Evaluation Criteria in Solid Tumors (RECIST) Version 1.1 (Eisenhauer et al 2009). Each patient will be evaluated for all potential sites of tumor lesions at screening/baseline and every 8 weeks after starting study treatment until disease progression.

CT (Computed Tomography) /MRI (Magnetic Resonance Imaging) scans will be performed at baseline within 28 days before start of treatment and subsequently every 8 weeks from treatment start until progression of disease.

After baseline, the first assessment should be performed at Cycle 3 Day 1 (+7 day window) and all subsequent assessments should be performed within ± 7 days of the scheduled day of assessment. The same method of assessment and the same technique should be used to characterize each individual and reported lesion at baseline and during follow-up. If a patient discontinues treatment for reasons other than radiological documentation of progression of disease, an efficacy assessment should be performed at the time of End of Treatment unless a CT/MRI for tumor measurement was performed ≤ 4 weeks earlier.

Chest, abdomen, and pelvis CT scans are required for all patients at baseline. If at baseline, a patient is known to have a contraindication to CT i.v. contrast media or develops a contraindication during the trial, a contrast-enhanced MRI (if possible) of chest, abdomen, and pelvis should be performed.

For the patients with skeletal lesions suspected at baseline, a whole-body bone scan (e.g. TC 99, NaF PET, etc.) should be performed. Skeletal lesions which are identified on a whole body bone scan at baseline, which are not visible on the chest, abdomen or pelvis CT/MRI scan, should be re-imaged at baseline with localized CT, MRI or x-ray, and followed at scheduled visits (every 8 weeks).

Partial Response (PR) and Complete Response (CR) should be confirmed by repeat assessments performed at least 4 weeks and no later than 6 weeks after the criteria for response are first met.

PET/CT may be used only if it is of similar diagnostic quality as a CT performed without PET, including the utilization of oral and intravenous contrast media. While FDG-PET may complement CT scans in assessing progression per RECIST 1.1 (Appendix 3) FDG-PET assessments should be disregarded for this protocol.

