10.1 Sample size and power calculation

For Cohort 1, the Simon optimum two-stage design is used to evaluate the primary endpoint of overall response rate in this patient population (Simon 1989; Simon et al. 2016). In this relapsed/refractory population of advanced solid tumor patients identified as having genomic fusion in *FGFR1-3*, our null hypothesis is that if the treatment is not active then the overall response rate will be at most 5%, reflecting a response by chance alone. We hypothesize that for this treatment, an ORR of at least 25% would be considered promising in this patient population. This study is designed to detect an ORR of at least 25% vs. $\leq 5\%$. After evaluating 9 patients enrolled in the first stage, the trial will be terminated if 0/9 patients demonstrate a response. If the trial goes on to the second stage, a total of 30 evaluable patients will be enrolled. If the total number responding is 4 or more, then the drug demonstrates promising response in this patient population. This design has 90% power and 5% type I error.

For Cohort 2 and 3, with $n=10$ evaluable patients, the estimated ORR with corresponding 90% Confidence Interval for various number of responses are listed below:

Responses	ORR	90% CI
0	0	(0.0, 0.206)
1	0.1	(0.005, 0.394)
2	0.2	(0.037, 0.507)
3	0.3	(0.087, 0.607)

4	0.4	(0.150, 0.696)
5	0.5	(0.222, 0.778)
6	0.6	(0.304, 0.850)
7	0.7	(0.393, 0.913)
8	0.8	(0.493, 0.963)
9	0.9	(0.606, 0.995)
10	1	(0.794, 1.000)

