13.3.5 Eligibility based on measurable disease

If no measurable lesions are identified at baseline, the patient may be allowed to enter the study in some situations (e.g. in Phase III studies where PFS is the primary endpoint). However, it is recommended that patients be excluded from trials where the main focus is on the Overall Response Rate (ORR). Guidance on how patients with just non-measurable disease at baseline will be evaluated for response and also handled in the statistical analyses is given in Section 13.3.25.

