13.3.25 Handling of patients with non-measurable disease only at baseline

It is possible that patients with only non-measurable disease present at baseline are entered into the study, either because of a protocol violation or by design (e.g. in Phase III studies with PFS as the primary endpoint). In such cases the handling of the response data requires special consideration with respect to inclusion in any analysis of endpoints based on the overall response evaluations.

It is recommended that any patients with only non-measurable disease at baseline should be included in the main (ITT) analysis of each of these endpoints.

Although the text of the definitions described in the previous sections primarily relates to patients with measurable disease at baseline, patients without measurable disease should also be incorporated in an appropriate manner. The overall response for patients with measurable disease is derived slightly differently according to Table 15.

Table 15: Overall lesion response at each assessment: patients with non-target disease only

Non-target lesions	New Lesions	Overall lesion response
CR	No	CR
Non-CR/Non-PD ¹	No	Non-CR/non-PD
UNK	No	UNK
PD	Yes or No	PD
Any	Yes	PD

¹ As defined in Section 13.3.8.

In general, the **non-CR/non-PD response** for these patients is considered equivalent to an SD response in endpoint determination. In summary tables for best overall response patients with only non-measurable disease may be highlighted in an appropriate fashion e.g. in particular by displaying the specific numbers with the non-CR/non-PD category.

In considering how to incorporate data from these patients into the analysis the importance to each endpoint of being able to identify a PR and/or to determine the occurrence and timing of progression needs to be taken into account.

For ORR it is recommended that the main (ITT) analysis includes data from patients with only non-measurable disease at baseline, handling patients with a best response of CR as “responders” with respect to ORR and all other patients as “non-responders”.

For PFS, it is again recommended that the main ITT analyses on these endpoints include all patients with only non-measurable disease at baseline, with possible sensitivity analyses which exclude these particular patients. Endpoints such as PFS which are reliant on the determination and/or timing of progression can incorporate data from patients with only nonmeasurable disease.

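### Inclusion criterion 4 admits patients without measurable disease to a trial with response rate as primary endpoint, against the advice of its own response guideline and without a stated reason

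*Combined protocol and SAP*

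**What the plan says.** The primary endpoint in Section 3.1 (Table 2) is "Overall response assessed by investigator as per RECIST v1.1". Inclusion criterion 4 in Section 5.2 requires "Evidence of measurable or evaluable disease according to RECIST Version 1.1". The same pairing of measurable or evaluable recurs in inclusion 5, in Section 5.1 and in the Protocol Summary (Inclusion criteria), there for patients whose earlier treatment was stopped for toxicity.

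Section 7.2.1 names the response rules: "Tumor response will be evaluated locally by the investigator according to the guideline (see Appendix 3". Three parts of Appendix 3 bear on this point:

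- Section 13.3.5, on patients with no measurable lesion at baseline: "the patient may be allowed to enter the study in some situations (e.g. in Phase III studies where PFS is the primary endpoint". It then says "it is recommended that patients be excluded from trials where the main focus is on the Overall Response Rate (ORR".
- Section 13.3.25, Table 15: for patients with non-target disease only, the possible overall responses are CR, non-CR/non-PD, UNK and PD. There is no PR. A non-CR/non-PD result "for these patients is considered equivalent to an SD response in endpoint determination".
- Section 13.3.25, on analysis: "For ORR it is recommended that the main (ITT) analysis includes data from patients with only non-measurable disease at baseline". A best response of CR counts as a response and anything else as a non-response.

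For Cohort 1, Section 10.1 uses a Simon two-stage design with a 5% null. It states "We hypothesize that for this treatment, an ORR of at least 25% would be considered promising in this patient population". The cohort stops at 0 responses in 9 and is called promising at 4 or more in 30, with 90% power and 5% type I error.

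On counting, Section 10.1 and the Protocol Summary (Data analysis) ask for a total of 30 evaluable patients. The Protocol Summary (Population) and Section 5.2 cap Cohort 1 at 30, Section 7.1.4.1 foresees no replacement, and Section 10.2 makes the Full Analysis Set (FAS, all dosed patients) the default for every analysis.

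**The concern.** A patient with only non-measurable disease cannot show the commonest form of response in a solid tumour trial, a partial response. Such a patient still occupies a place in the stage 1 group of 9, in the 30 of Cohort 1, or in the 10 of Cohort 2 or 3, where one patient is 10% of the denominator. No analysis set removes them. The FAS keeps everyone dosed, and under Section 10.2 a single non-CR/non-PD assessment is enough to be evaluable for efficacy.

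At stake is the chance of missing activity. The 0/9 rule stops the trial and the 4-responder rule decides whether the drug is called promising in Cohort 1. The guideline the trial adopted foresees this and advises against it for a trial of this kind.

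The smaller matter is that the plan does not say in which set the 9 and the 30 are counted. With a cap of 30 and no replacement, a single unassessed patient makes 30 evaluable patients unattainable.

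**Working it through.** **Inputs from Section 10.1.** Null ORR 5%, target ORR 25%, stop at 0/9, success at 4 or more of 30 (21 patients in stage 2).

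**Step 1: reproduce the stated design.** With X1 ~ Bin(9, p) and X2 ~ Bin(21, p):

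P(success) = Σ over x = 1 to 9 of P(X1 = x) × P(X2 ≥ 4 − x)

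| Stage 1 responses | p = 25% | p = 5% |
|---|---|---|
| 1 | 0.2253 × 0.9255 = 0.2085 | 0.2985 × 0.0849 = 0.0254 |
| 2 | 0.3003 × 0.9810 = 0.2946 | 0.0629 × 0.2830 = 0.0178 |
| 3 | 0.2336 × 0.9976 = 0.2330 | 0.0077 × 0.6594 = 0.0051 |
| 4 or more | 0.1657 | 0.0006 |
| **Total** | **0.902** | **0.0489** |

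The false stop at stage 1 is 0.75^9 = 0.0751. The stated 90% power and 5% type I error are reproduced. There is little slack: power falls below 90% once the overall ORR is under 24.9%.

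**Step 2: if 25% is the ORR of everyone admitted.** Power is 90.2% as above. The target then implies a higher rate in patients with measurable disease. If k of 30 have none and no CR occurs among them, that rate is 0.25 × 30/(30 − k): 25.9%, 26.8% or 27.8% for k = 1, 2 or 3.

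**Step 3: if 25% is the ORR in measurable patients only.** The documents give no share without measurable disease, so k = 1, 2, 3 is an assumption. Let j of the k fall by chance among the first 9:

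P(j) = C(k, j) × C(30 − k, 9 − j) / C(30, 9)

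With a zero CR rate in these patients, the false stop is Σ P(j) × 0.75^(9 − j). For k = 1: 0.7 × 0.0751 + 0.3 × 0.1001 = 0.0826. Power uses the sum in Step 1 with 9 − j and 21 − (k − j) patients able to respond, averaged over P(j).

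| k of 30 | Power, CR rate 0 | False 0/9 stop, CR rate 0 | Power, CR rate 5% |
|---|---|---|---|
| 0 | 90.2% | 7.5% | 90.2% |
| 1 | 88.9% | 8.3% | 89.2% |
| 2 | 87.6% | 9.1% | 88.1% |
| 3 | 86.0% | 10.0% | 86.9% |

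**Step 4: type I error.** With 5% in measurable patients and 0 in the others, it is 4.4%, 3.9% or 3.5% for k = 1, 2 or 3. It falls.

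**Step 5: the counting set.** Section 10.4.1 names no set for ORR, so the Section 10.2 default (FAS) applies. Thirty dosed patients fit the cap and the no-replacement policy. Thirty evaluable patients fit only if none goes unassessed. The success rule counts responders, and a patient with no assessment cannot be one, so the count of 4 or more among the same treated patients is the same either way. What stays open is who the first 9 are.

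**The case against.** Section 13.3.5 is advice, and its Phase III example is not exhaustive. Appendix 3 is a generic guideline that leaves study-specific decisions to the protocol (Section 13.3.28). The phrase appears in several places, which suggests a choice rather than a slip. Section 13.3.25 foresees such patients entering by design and says how to count them, conservatively. They also still inform PFS, disease control and survival. All of this stands. It means that nothing is undefined and no rule is broken. It does not supply a reason for the choice, and a counting rule does not make a partial response possible.

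A reader might infer that the stated 90% power is wrong. The documents do not support that. Section 10.1 speaks of the ORR in this patient population, which on its plain reading is everyone admitted, and then 90.2% is correct. Every lower figure in Step 3 needs the narrower reading plus an assumed count and CR rate.

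A reader might also infer that the choice between evaluable and treated patients could change the success verdict or the planned confidence interval. It does not. Section 10.2 makes the FAS the set for ORR, no evaluable-only analysis is planned, and success rests on the number of responders, not on where an interval limit falls.

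**Conclusion.** The point holds as a cheap improvement. The trial admits patients who can respond only by CR, its own guideline recommends leaving them out when ORR is the main focus, and no reason is given for doing otherwise.

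The size is modest and conditional: about 1 to 4 points of power and up to 2.5 points more risk of a false 0/9 stop, for an assumed 1 to 3 of 30 such patients with no CR and a 25% target meant for measurable disease. If 25% describes the whole admitted population, the stated power stands, and the cost is that measurable patients must do somewhat better than 25%. The wording is certain; how many such patients would enroll is unknown.

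The mismatch over 30 evaluable patients is real but minor and editorial.

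**What to change.** 1. Change inclusion 4 to: *At least one measurable lesion per RECIST Version 1.1*, for all three cohorts. Align the measurable-or-evaluable wording in inclusion 5, Section 5.1 and the Protocol Summary, so that no conflicting text remains.
2. In Section 10.1 and the Protocol Summary (Data analysis), replace the reference to 30 evaluable patients with: *The 0/9 and 4/30 rules apply to the first 9 and to all 30 treated Cohort 1 patients (FAS); patients without a post-baseline response assessment count as non-responders.* This settles who the first 9 are and leaves the 4-responder rule as it is.

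The cost is wording, plus the loss of patients with only non-measurable disease. The documents do not say how many there are, and accrual in a rare molecular group may be slightly slower. The second edit does not remove the effect of unassessed patients; it makes their handling explicit. The two edits are independent, and neither solves the other's problem.
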